## 5.0 SUBJECT SELECTION

### 5.1 Inclusion Criteria

- 5.1.1 Patients >18 years old.
- 5.1.2 Women of child-bearing age must have a negative pregnancy test.
- 5.1.3 Patients must have received prior radiation treatment to the chest. Records of prior radiation treatment must be available.
- 5.1.4 Patients must have received prior chest radiation at least 3 months prior to enrollment in this trial. Radiation treatment to other body sites not overlapping with current radiation fields are allowed within the 3 months period (example, brain radiation is allowed).
- 5.1.5 Patients must have a prior diagnosis of cancer inside the thoracic cavity. Both primary thoracic malignancies (such as lung cancer) as well as metastatic lesions (such as metastatic breast cancer or colorectal cancer to the lungs) are allowed. Patient must have pathologic confirmation of the recurrent thoracic tumor, or have an enlarging thoracic mass (as seen on two CT scans at least 6 weeks apart, with either a >25% or >5 mm increase in longest dimension).
- 5.1.6 Patients must have a life expectancy of > 6 months.
- 5.1.7 Patients must have measurable disease to be treated with proton radiation (minimum tumor dimension at least 10 mm on CT imaging).
- 5.1.8 Patients should have either non-metastatic cancer of the thorax, or metastatic cancer to the thorax and candidate for definitive radiation dose to the thoracic tumor (not palliative intent), tumor radiation dose to at least BED2Gy 60 Gy.
- 5.1.9 Patients must be able to receive proton radiation treatment.
- 5.1.10 All stages of cancer are eligible.
- 5.1.11 There are no limits on prior therapy. Patients are allowed to have prior chemotherapy and surgery. Patients are allowed to have concurrent chemotherapy with radiation treatment. Patients are allowed to have chemotherapy or surgery after radiation treatment.
- 5.1.12 Patients are allowed to be on another study concurrent with this protocol.
- 5.1.13 Ability to understand and the willingness to sign a written informed consent document.

## 5.2 Exclusion Criteria

- 5.2.1 Patients who have never received radiation to the chest.
- 5.2.2 Patients who received radiation to the chest within the past 3 months (in a region that overlaps with current radiation fields).
- 5.2.3 Patients with life expectancy < 6 months.
- 5.2.4 Pregnant women.
- 5.2.5 Patients unable to provide informed consent.
- 5.2.6 Prisoners.

## 5.3 Recruitment

Subjects will be recruited from investigator clinical practices and include men and women **with recurrent thoracic cancer** who will be receiving radiotherapy to at least BED2Gy 60 Gy. Subjects will undergo an informed consent process in accordance with GCP. Informed consent will be obtained prior to the performance of any screening procedures.

## 6.0 SUBJECT REGISTRATION

Subjects will be registered by the FHCRC/UW Study Coordinator and entered into the Protocol Accrual Tracking System (PATS). Information regarding the PATS system is available at [http://www.cancerconsortiumorg/rto/protocol\\_office/pats/](http://www.cancerconsortiumorg/rto/protocol_office/pats/). A complete, signed, study consent and HIPAA consent are required for registration.

## 7.0 TREATMENT PLAN

All patients will receive radiation treatment per standard of care, adhering to the normal organ radiation dose constraints outlined in this protocol. The only additional procedure related to this protocol is informed consent at enrollment.

The standard treatment outline for patients receiving radiation treatment, which also applies to patients on this protocol, begins with an initial consultation, including history and physical. Patients' prior radiation records will be obtained and reviewed. If patients are eligible and consent to repeat irradiation, they are scheduled for a radiation simulation scan, to be used for radiation treatment planning. Physicians will delineate the target tumor volume as well as normal organs to be protected in the region. A radiation plan will be generated that meets the normal organ dose limits outlined in this protocol. The plan undergoes quality assurance checks, and patients then start treatment. During treatment, patients are seen at least once weekly by the physician to assess for toxicity. After completion of radiation, patients are seen typically 3 months post-treatment with CT chest to assess for treatment response and toxicity. Additional imaging or follow up visits may take place per routine medical standard of care. Research staff will review clinical record at 3 months post-treatment. See Table 1 below for summary.

**Table 2. Study Calendar.**

	Screening	Prior to Start of Radiation Treatment	Weekly During Radiation Treatment	3-Months*** Post-Radiation Treatment End
Informed Consent	X*			
Physical Exam	X		X	X
Medical History	X		X	X
Pulmonary Function Tests (PFTs)		X		X
CT Chest	X			X
Serum Pregnancy Test**	X			

\* Denotes a Research Procedure, all others are standard of care

\*\* For women of child bearing potential only

\*\*\* Exact time of follow up can vary depending on clinical judgment. Patients are typically seen at 3 months after treatment, but this can vary between 2-6 months as judged appropriate by treating physician.

## 7.1 Radiation Treatment Parameters

### 7.1.1 Localization, Simulation, and Immobilization

Body cradle or similar immobilization device(s) must be utilized. A treatment planning CT scan is mandatory. CT scan thickness should be 0.5 cm or smaller (preferably  $\leq 0.3$  cm) through the treatment volume. Intravenous contrast is recommended in patients who do not have a contraindication to it. MRI and/or PET scans with image fusion also may be helpful in treatment planning, particularly if these scans can be performed with the same immobilization device as was used for the planning CT scan. 4D CT scan with respiratory motion tracking is strongly preferred for lung tumors. Any tumors moving more than 1 cm with respiration must be considered for motion management for radiation treatment, which can include but not limited to: abdominal compression, respiratory gating, and active breathing control. These are all standard of care for lung radiation treatment.

### 7.1.2 Volume Definitions

**Gross Tumor Volume (GTV):** This is the region of interest that is known to contain gross cancer. This will include all gross tumor as based upon the planning CT scan. This also may include areas that appear “normal” by the planning CT scan but are known to harbor cancer based on the MRI, PET, physical examination, endoscopy, etc.

**Clinical Tumor Volume (CTV):** The CTV is defined to be the GTV plus a margin as appropriate to account for microscopic tumor extension. The exact CTV margin to be used is at the discretion of the treating physician, and can be as low as 0 mm if microscopic extension is not felt to be of concern in a particular patient situation.

**Internal Target Volume (ITV):** If 4D CT scans are used to assess for breathing motion, the ITV will be used to encompass the CTV and all respiratory motion.

**Planning Tumor Volume (PTV):** This includes the CTV (or ITV if appropriate) plus a margin to compensate for various uncertainties, such as systematic treatment setup variables, organ motion (especially with respiratory motion), and organ displacement. A minimum of 5 mm around the CTV is required in all directions, except where the CTV is immediately adjacent to a critical organ such as the spinal cord (in which case, the margin from CTV to PTV may be as small as 1 mm).

### 7.1.3 Treatment Planning Dose Constraints

- A composite radiation plan that includes the prior thoracic radiation must be generated.
- Minimum PTV dose should be 90% of the prescription dose and 95% of the PTV should receive the prescription dose, unless PTV overlaps with a critical normal organ. In that case, the portion of PTV not overlapping with the critical organ should meet the constraint above. Min PTV dose <80% will be a major violation, volume of PTV receiving prescription dose <90% will be a major violation.
- Minimum prescription dose to PTV must be at least BED2Gy 60 Gy.
- Spinal cord: max point dose 50 Gy (<0.03 cc) or BED equivalent (BED2Gy 83 Gy) from proton radiation plan. Composite maximum spinal cord dose must not exceed BED2Gy 90 Gy. For patients who received radiation > 3 years prior, the cord constraint can be increased with PI approval.
- Normal lung: mean dose < 20 Gy and volume receiving 20 Gy (V20) < 35% for proton radiation plan.
- Esophagus: mean dose <34 Gy and max dose < 66 Gy for proton plan. Composite max point dose < BED2Gy 140 Gy.
- Heart: mean dose < 40 Gy and max dose < 66 Gy for proton plan. Composite max point dose < BED2Gy 140 Gy.

### 7.1.4 Treatment delivery

All patients will have daily imaging guidance for setup and positioning prior to proton radiation delivery. This is typically done with port films.

### 7.1.5 R.T. Quality Assurance Reviews

All patients treated on this protocol will undergo standard review in the Department of Radiation Oncology. At least two physicians will review the patient history, imaging findings, tumor contours, and radiation plan.

### 7.1.6 Radiation Toxicity

Toxicity will be graded based on CTCAE 4.0. Grade two and above adverse events will be recorded in a Redcap database. The AE's will be followed for three months post-treatment.

## 7.2 Criteria for Removal/Withdrawal from Treatment

Patients will be withdrawn from treatment if their clinical conditions decline so they are no longer able to tolerate proton radiation, or are unlikely to clinically benefit from further therapy.

Patients will still receive follow up care per standard of care even if they withdraw from the study. If a subject withdraws consent to participate in the study or aspects of the study, attempts will be made to obtain permission to record at least survival data up to 6 months post-treatment.

## 8.0 DATA AND SAFETY MONITORING PLAN

Oversight for this study at the SCCA and UWMC will be provided by the Principal Investigator with delegation of appropriate responsibilities to sub-investigators and designated study personnel. They will ensure all entry criteria are met prior to the initiation of the protocol and all study procedures and reporting of adverse events are performed according to the IRB-approved protocol.

## 8.1 Early Stopping Rules

In the event of a grade 5 event occurring within  $\leq 30$  days after the end of treatment, there will be a temporary cessation in patient enrollment for event review. If the event is defined as possibly, probably, or definitely related to treatment (per CTCAE, v.4.0), early stopping of this trial will occur permanently. All Grade 3 and 4 AE's will be immediately monitored and reviewed by PI.

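### The only rule that halts enrolment covers deaths up to 30 days after treatment, but no contact or status check is scheduled until 2-3 months, so a triggering death can be learned of late

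*Combined protocol and SAP*

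**What the plan says.** **The rule.** Section 8.1 (Early Stopping Rules) applies to a grade 5 event up to 30 days from the end of treatment: "there will be a temporary cessation in patient enrollment for event review". If the event is judged at least possibly related to treatment, "early stopping of this trial will occur permanently". For lower grades there is no halting threshold, but "All Grade 3 and 4 AE's will be immediately monitored and reviewed by PI". Section 10.0 repeats the grade 5 rule and gives an 88% chance of triggering it if the true grade 5 rate is 10%.

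**What is scheduled.**
- On treatment (Section 7.0): "During treatment, patients are seen at least once weekly by the physician to assess for toxicity".
- After treatment, visit (Table 2 footnote): "Patients are typically seen at 3 months after treatment, but this can vary between 2-6 months as judged appropriate by treating physician".
- After treatment, records (Section 7.0): "Research staff will review clinical record at 3 months post-treatment".
- Anything else (Section 7.0): "Additional imaging or follow up visits may take place per routine medical standard of care".

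**General duties.** Section 7.1.6 has adverse events of grade 2 and above entered in a database and followed for three months, with no contact points inside that period. Section 8.0 makes the PI and delegated staff responsible for adverse event reporting. Section 8.2 provides reports twice a year. None of these sets a date for checking a patient's status near day 30, or says how and how fast a death reaches the PI.

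**The concern.** A pause in enrolment protects the next patient only if the team knows that the event has happened. The trigger window closes at day 30, while the first scheduled look at a patient after treatment comes at 2 months at the earliest. A patient who dies at home or in another hospital on day 20 need not come to the study team's notice until the 3-month record review or a missed visit. In the meantime the trial may go on enrolling, although its own rule calls for a halt.

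The rule is strict: one related death ends the trial. It is also the only rule that halts enrolment, so its value depends on prompt knowledge. Immediate PI review of grade 3-4 events has the same weakness once treatment is over, because no scheduled step brings such an event to light.

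**Working it through.** **1. The plan's own figure.** Section 10.0: n = 20, true grade 5 rate 10%.
P(at least one event) = 1 - 0.9^20 = 1 - 0.1216 = 0.878. The stated 88% reproduces. Time does not enter the formula.

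**2. Delay from death to first scheduled check.** Take the death on day 0 to day 30 after the end of treatment, and 30.4 days per month. Delay = day of check - day of death.

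| First scheduled check | Day of check | Delay, death on day 30 | Delay, death on day 0 |
|---|---|---|---|
| Visit at 2 months | 61 | 31 days | 61 days |
| Record review at 3 months | 91 | 61 days | 91 days |

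The scheduled delay is therefore about 1-3 months, and about 2-3 months when the 3-month review is what finds the death. Deaths during the radiation course should surface through the weekly visits, so the gap concerns the 30 days after it.

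**3. Accrual rate (assumption).** Section 1.0 gives a study duration of 3 years and 20 evaluable subjects, but no accrual period. With even accrual:
- over 36 months: 20/36 = 0.56 patients per month
- over 24 months: 20/24 = 0.83 patients per month

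**4. Patients enrolled between the death and the 3-month review** (2.0 to 3.0 months):
- 36 months: 0.56 × 2.0 = 1.1 to 0.56 × 3.0 = 1.7
- 24 months: 0.83 × 2.0 = 1.7 to 0.83 × 3.0 = 2.5

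If accrual took only 12 months (1.67 per month), the range would be 3.4 to 5.0.

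**5. Gain from a day-30 (+7) check.** The fair comparison is with the proposed check, not with instant knowledge. For a death on day 20 and a review at about day 90:
- check on day 30: 90 - 30 = 60 days earlier
- check on day 37: 90 - 37 = 53 days earlier

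In patients:
- low: (53/30.4) × 0.56 = 1.74 × 0.56 = 1.0
- high: (60/30.4) × 0.83 = 1.97 × 0.83 = 1.6

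**6. Cross-check by simulation.** Assumptions: uniform accrual, 1.5 months from enrolment to end of treatment, a 10% grade 5 rate, death uniform over days 0-30, and every death unnoticed until the scheduled check. Mean number enrolled when enrolment stops:

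| Accrual period | Found at 3 months | Found at day 30 | Difference |
|---|---|---|---|
| 36 months | 10.9 | 10.0 | 0.9 |
| 24 months | 11.9 | 10.5 | 1.4 |
| 12 months | 14.7 | 12.2 | 2.5 |

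For 24-36 months this agrees with step 5.

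**The case against.** **The team would often hear sooner.** Section 7.1.6 obliges follow-up of adverse events through the whole 30-day window, Section 8.0 assigns reporting, and Section 5.3 recruits from the investigators' own practices, so treating physicians and study team overlap. This stands as a limit on size: the figures above assume that the death escapes notice until a scheduled check, and are close to a ceiling for those accrual rates. It does not close the gap, because none of these duties carries a date or a notification route.

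**Treatment is standard of care.** Section 7.0 says that consent is the only added procedure. The documents do not show how far a pause would change the treatment of a patient who presents in the interval. That also stands. The gain can be counted in enrolments, not in treatments avoided.

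**A delay of up to six months.** Because the visit may fall at month 6, a reader might infer that a day-20 death could stay unknown for about 180 - 20 = 160 days, with 3-4 more patients enrolled in roughly 5 months. The documents do not support this as the scheduled delay. The 2-6 month range belongs to the visit; the record review is set at 3 months whatever the visit date. The longer delay arises only if that review also misses the death.

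**The 88%.** A reader might also infer that late detection makes this figure wrong. It does not: the figure is the chance of at least one event in 20 patients, whenever it becomes known. It would fall only if some qualifying deaths were never found (to 79% if three quarters were found, 1 - 0.925^20), and nothing in the documents supplies such a share.

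**Conclusion.** The concern holds in a limited form. The plan sets a 30-day trigger without a scheduled step that would reveal it in time, and as written it can keep enrolling for about 1-3 months after a triggering death that routine care does not bring to light. Against the 3-month review, a day-30 (+7) check saves about 53-60 days for a day-20 death, or roughly 1-2 patients out of 20.

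The patient count rests on an assumed even accrual over 24-36 months and would be larger if accrual were faster. No toxicity or local control cut-off in Section 10.0 is affected. This is a cheap safety improvement, and it is worth making because a single related death is meant to end the trial.

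**What to change.** Add a column to Table 2 at 30 days (+7) after the end of radiation: vital status and grade 3 or higher adverse events, obtained by telephone from the patient or family and supplemented by chart review, done by the existing research staff. The window should open on day 30, not before, so that it covers the whole period in Section 8.1. Direct contact is needed because a chart check alone may miss a death at home or in another hospital.

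Add to Section 8.1 or 8.0 that any death found is reported to the PI at once, so that the pause can take effect, and that grade 3-4 events found at the call go to the PI in the same way. The trigger and the relatedness criteria stay as they are.

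**Cost.** One short call per patient (20 in total) and a minor amendment, with no added clinic visit, scan or laboratory test. The Section 7.0 statement that consent is the only additional procedure, and the Table 2 footnote that marks research procedures, need updating. With the check in place, a death on day 1 would be found at most 37 - 1 = 36 days later.

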### 4.2 Endpoints

#### 4.2.1 Primary Endpoint

Grade 3 or greater toxicity attributable to radiation treatment.

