## 8.2 Interim Data Review

Interim reports with statistical analyses will be prepared twice per year until the initial treatment results have been presented or published. In general, the interim reports will contain the following information:

- Patient accrual rate with a projected completion date (while the study is still accruing)
- Total patients accrued
- Frequencies and severity of adverse events
- Compliance rates of treatment delivery

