## 10.0 STATISTICAL CONSIDERATIONS

The primary objective of this protocol is to provide a preliminary evaluation of the safety and efficacy of re-irradiation with proton beam radiotherapy in patients with recurrent thoracic cancer. Ideally this therapy should have a grade 3 toxicity rate of < 25% and a local control rate of > 80%.

Twenty patients will be enrolled. If 7 or more of the 20 patients experience grade 3 toxicity, then we would be at least 80% confident that the true toxicity rate exceeds 25%; conversely, if 3 or fewer of the 20 patients experience grade 3 toxicity, then we would be at least 80% confident that the true toxicity rate is less than 25%. An intermediate result, 4-6 patients with grade 3 toxicity, would be regarded as inconclusive.

With regard to efficacy, if the therapy results in 14 or fewer of the 20 patients with local tumor control, then we would be at least 80% confident that the true local control rate is less than 80%; conversely, if 18 or more of the patients have local tumor control, then we would be at least 80% confident that the true local control rate exceeds 80%. An intermediate result, 15-17 patients with local tumor control, would be regarded as inconclusive.

An early stopping rule will be imposed for grade 5 adverse events, and the protocol will stop should any patients experience a grade 5 AE as described in Section 8.1. If the true rate of grade 5 AE is 10%, then there is an 88% chance that this stopping rule will be triggered.

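### No accrual action is tied to the 7-of-20 grade 3 toxicity count that Section 10 reads as unfavourable; a pause for review at the 7th case would be a cheap improvement

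*Combined protocol and SAP*

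**What the plan says.** Section 4.2.1 defines the primary endpoint as "Grade 3 or greater toxicity attributable to radiation treatment". Section 10 sets the sample at 20 and gives three readings of the toxicity count. "If 7 or more of the 20 patients experience grade 3 toxicity", the plan claims at least 80% confidence that the true rate is above 25%; 3 or fewer supports a rate below 25%; 4 to 6 is inconclusive.

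Section 8.1 contains the only accrual action. A grade 5 event within 30 days after treatment pauses enrolment for review, and if it is judged at least possibly related, "early stopping of this trial will occur permanently". Grade 3 and 4 events "will be immediately monitored and reviewed by PI", with no count and no stated consequence.

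Section 8.2 says "Interim reports with statistical analyses will be prepared twice per year". Their listed content includes "Frequencies and severity of adverse events", again with no threshold or action. Section 10 names no early stopping rule other than the grade 5 one.

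**The concern.** The number of affected patients can only rise as more are enrolled. Once a 7th patient has a qualifying event, the final count must lie in the range that Section 10 treats as unfavourable, and no later patient can move it back to inconclusive. The plan nevertheless allows accrual to run on to 20, subject only to the PI's judgement. Because this is the primary endpoint, and a safety endpoint, a stated count would make a pause predictable instead of case by case. At stake are the patients who would be enrolled after the plan's own safety reading is already settled.

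**Working it through.** **Inputs from the documents.** N = 20, the cut-off of 7 and the 25% reference rate (Section 10); AE follow-up of three months after treatment (Section 7.1.6); a follow-up visit that may fall at 2 to 6 months (Table 2 footnote); study duration of 3 years (Section 1.0).

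**Assumed.** True rates of 15% to 50% for illustration; 1.5 months of treatment; accrual over 18 to 32 months, since the documents give no accrual rate; cases becoming known in order of enrolment.

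**1. The plan's own figures.** Grade 5 rule at a true rate of 10%: 1 − 0.9^20 = 0.878, matching the stated 88%. Confidence at 7 of 20 that the rate exceeds 25%: exact binomial P(X ≤ 6 | 20, 0.25) = 78.6%; mid-P 84.2%; score 84.9%. The stated 80% therefore holds under the less conservative methods and misses by 1.4 points under the exact one. At 6 of 20 the exact figure is 61.7%, so 7 is the natural cut-off.

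**2. How often the pause would be reached.** P(X ≥ 7 | 20, p) is 2.2% at p = 0.15, 21.4% at 0.25, 75.0% at 0.40 and 94.2% at 0.50. The pause adds no new threshold: these are also the shares of full 20-patient trials that would end in the unfavourable range.

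**3. The recognition lag L**, meaning patients enrolled between the 7th case and its recognition.
- Delay 1.5 + 3 = 4.5 months: 20/32 × 4.5 = 2.8 patients, up to 20/18 × 4.5 = 5.0.
- Visit at 6 months, delay 1.5 + 6 = 7.5 months: 20/32 × 7.5 = 4.7 patients, up to 20/18 × 7.5 = 8.3.
- Events seen at the weekly visits during treatment would shorten the lag, towards 0.

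**4. Enrolments avoided if accrual ends at the pause.** Let T be the patient number of the 7th case, with P(T = n) = C(n−1, 6) p^7 (1−p)^(n−7). The mean number avoided is the sum over n of max(0, 20 − n − L) × P(T = n). The chance of avoiding at least one is P(T ≤ 19 − L).

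| True rate | Lag 0 | Lag 3 | Lag 5 | Lag 8 |
|---|---|---|---|---|
| 25%: mean avoided | 0.65 | 0.23 | 0.09 | 0.01 |
| 40%: mean avoided | 3.62 | 1.75 | 0.88 | 0.19 |
| 40%: at least one avoided | 69% | 47% | 31% | 10% |
| 50%: mean avoided | 6.17 | 3.54 | 2.07 | 0.58 |
| 50%: at least one avoided | 92% | 77% | 60% | 27% |

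The saving is limited because the 7th case comes late: when it occurs within 20 patients, it is on average about patient 15 at 40% and patient 17 at 25%.

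**5. Statistical cost if accrual ends at the pause.** At lags 0, 3 and 5:
- The mean observed toxicity rate is 0.427, 0.413 and 0.407 at a true 0.40, and 0.534, 0.519 and 0.512 at a true 0.50.
- The SD at 0.40 is 0.139, 0.125 and 0.119, against sqrt(0.4 × 0.6 / 20) = 0.110 with 20 patients.
- The trial ends below 18 patients, so the favourable local-control cut-off cannot be met, with probability P(T ≤ 17 − L): 55%, 31% and 16% at 40%; 83%, 60% and 39% at 50%.

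**The case against.** The strongest case against has four parts.

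- **Existing oversight may be enough.** The PI reviews every grade 3 and 4 event, AE tables appear twice a year, and in a 20-patient pilot the PI will notice a 7th case. This stands in part: a discretionary pause is already possible. It does not make the response predictable.
- **The savings are not those of a pause.** This stands. If review lets accrual resume, enrolment returns to 20 and nothing is saved, so every figure in the table is an upper bound. The lag range must also reach about 8 patients, because the visit may come as late as 6 months.
- **Fewer enrolments may not mean fewer exposures.** This stands. Section 7.0 says "All patients will receive radiation treatment per standard of care" and adds "The only additional procedure related to this protocol is informed consent at enrollment". A patient not enrolled might still be re-irradiated, and Section 2.4 presents adherence to strict organ dose limits as the benefit of enrolling.
- **The change is not free statistically.** The bias, loss of precision and loss of local-control data are real, but they arise only if review ends accrual.

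A reader might infer that Sections 8.1 and 10 contradict each other. They do not: Section 10 uses the count only to interpret the result and never promises an accrual action. A reader might also infer that the trial should stop permanently at the 7th case. The documents do not support that either: Section 10 calls the evaluation preliminary, and exact confidence at 7 of 20 is 78.6%. A review fits that strength of evidence better than an automatic stop.

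**Conclusion.** The point holds as a suggested improvement, not as an error in the plan. No section ties a grade 3 count to accrual, although the 7th case already settles the Section 10 reading. A pause for review would rarely be reached at a true rate of 15% (2.2% of trials) and usually at 40% or 50% (75.0% and 94.2%).

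The benefit is modest: at most 3.62 enrolments avoided on average at 40% and 6.17 at 50%, falling to 0.19 and 0.58 at a lag of eight, and close to nothing at 25%. These sizes rest on the assumed accrual period, treatment length and order of recognition, and on review ending accrual. They count enrolments, not exposures.

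How to read a trial that ends below 20 patients is a separate gap. It already exists because of the grade 5 rule, and the case for the pause does not depend on it.

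**What to change.** 1. In Section 8.1, add that accrual pauses for review once a 7th patient has grade 3 or greater toxicity attributable to radiation. Name the Section 4.2.1 endpoint explicitly, because Section 10 says only grade 3.
2. In Section 8.2, add the running count of such patients to the twice-yearly reports.
3. In Section 10, state that if accrual ends early the toxicity reading at 7 stands, while the observed toxicity rate and local control are reported descriptively. The local-control cut-offs of 14 and 18 assume 20 patients.

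The certain cost is a short amendment. The data are already collected, since Section 7.1.6 records events of grade 2 and above. At a true rate of exactly 25%, 21.4% of trials would go to review. The statistical costs in step 5 of the working apply only if the review ends accrual.
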